## LIST OF ABBREVIATIONS

ACCORD	Academic and Clinical Central Office for Research & Development - Joint office for University of Edinburgh and NHS Lothian
AE	Adverse Event
AR	Adverse Reaction
CI	Clinical Investigator
ECG	Electrocardiogram
HASTE	Half Fourier Acquisition Single Shot Turbo Spin Echo
ISF	Investigator Site File
MEMRI	Manganese Enhanced Magnetic Resonance Imaging
ML	Millilitres
MRI	Magnetic Resonance Imaging
MG	Milligrams
NHS	National Health Service
PROBE	Prospective Randomised Open-label Blinded Endpoint
PI	Principal Investigator
SAR	Serious Adverse Reaction
SOP	Standard Operating Procedure
SUSAR	Suspected Unexpected Serious Adverse Reaction

## INTRODUCTION

### 1.1 BACKGROUND

#### 1.1.1 Takotsubo Cardiomyopathy

Takotsubo cardiomyopathy is an acute potentially fatal cardiac emergency that presents with sudden severe left ventricular dysfunction. It predominantly affects middle aged (50-74 years) women (90%) [Pattisapu et al, 2021] and is triggered by emotional or physical stress. Its symptoms are indistinguishable from acute myocardial infarction and 1 in 10 will die in hospital. However, patients with takotsubo cardiomyopathy have unobstructed coronary arteries, transient severe acute left ventricular dysfunction with “ballooning” of the ventricular cavity and absence of any myocardial infarction or scarring. Greater diagnostic recognition has led to a 4-5-fold rising incidence of takotsubo cardiomyopathy in both the United Kingdom and North America. With an incidence of 5,000 cases/year in the United Kingdom, it now represents 5% of all admissions for presumed myocardial infarction. [Singh et al, 2022]

Patients who recover from an acute takotsubo episode have substantially reduced long-term survival [Templin et al, 2015; Tornvall et al, 2016; Uribarri et al, 2019; Redfors et al, 2021]. Our own 5-year data of 620 patients in the Scottish Takotsubo Registry [Rudd et al, 2024] demonstrated a major excess of all-cause mortality compared with a 1:4 age and sex-matched general population (25% versus 15%; hazard ratio 1.78,  $p < 0.0001$ ). Importantly, this reduced survival was principally driven by cardiovascular mortality. In addition to mortality, there is also a substantial burden of morbidity with many patients experiencing hospitalisation for a recurrent takotsubo episode, stroke or myocardial infarction. In the international multicentre InterTak Registry, patients with takotsubo cardiomyopathy experienced a rate of major adverse cardiac and cerebrovascular events of 9.9% per patient-year, and a rate of death of 5.6% per patient-year [Templin et al, 2015]. This is consistent with our own data which showed that patients with takotsubo cardiomyopathy have 5-fold higher rates of major adverse cardiovascular events than the general population: hospitalisation for heart failure (9.8%), myocardial infarction (7.1%), stroke (3.9%) and recurrent takotsubo cardiomyopathy (10.2%).

Despite left ventricular ejection fraction recovering to normal during convalescence, persistent sub-clinical cardiac dysfunction has been consistently demonstrated [Sally et al, 2018]. Some patients continue to have debilitating symptoms like those with heart failure (fatigue, breathlessness, chest pain) which reduce their quality of life and cause at least one further hospital admission each year [NHS England]. Many have multiple recurrent episodes of takotsubo cardiomyopathy. A Swedish study reports an average cost of €10,360 to the health system in the first 6 months after a takotsubo diagnosis, with patients using repeated hospital, outpatient and primary care

resources [Wallstrom et al, 2019]. This would equate to over £50 million per annum across the United Kingdom, but the total burden to the NHS will be much higher considering the ongoing elevated risk of events beyond 6 months.

### **1.1.2 Detection of subclinical myocardial dysfunction**

The observation that left ventricular dysfunction and reduced left ventricular ejection fraction rapidly recovers after an acute takotsubo episode (a characteristic feature of this condition) is often falsely reassuring for both the patient and the clinician. It also means that detection of residual left ventricular dysfunction despite apparent normal standard clinical assessments of contractile function can be challenging. We have previously demonstrated impaired myocardial cardiac energetic status using magnetic resonance spectroscopy [Sally et al, 2018]. We then went on to explore whether this perturbation in energetics influenced myocardial contractile performance through alterations in myocardial calcium handling.

### **1.1.3 Manganese-enhanced magnetic resonance imaging**

Manganese is a naturally occurring essential trace element, required by the human body as a co-factor and enzyme activator [Frayn, 2010; Santamaria, 2008]. Its role has been demonstrated in the normal metabolic functioning of multiple organs in addition to the protection of mitochondrial membranes from oxidative stress via superoxide dismutase [Santamaria, 2008]. Manganese exhibits certain advantageous properties that make it a potentially powerful tool in magnetic resonance imaging. First, its paramagnetic properties reduce the T1 relaxation times of water, providing positive contrast in tissues where it accumulates, and excellent delineation of anatomical structures [Massaad & Pautler, 2010; Pan et al, 2010]. Second, it is a calcium analogue and is taken up by voltage-gated calcium channels and sodium-calcium exchangers on active viable myocytes [Du et al, 2001]. This is an active process which allows manganese to differentiate regions of altered myocyte function and, in combination with T1 mapping protocols, can be used to quantify myocardial calcium handling. Manganese therefore presents attractive opportunities both in terms of the practicalities of imaging and the tracking of active biological processes.

As part of a previous British Heart Foundation-funded Clinical Research Training Fellowship ([name], FS/17/19/32641), we have shown that manganese-enhanced magnetic resonance is a better measure of myocardial infarction size than late gadolinium enhancement [Spath et al, 2018] and, using T1 mapping, we have described altered manganese uptake in patients with dilated cardiomyopathy [Spath et al, 2020] (Figure 1).

### **1.1.4 Magnetic resonance imaging in takotsubo cardiomyopathy**

[figure not shown]
Using magnetic resonance imaging, we have previously reported the presence of severe global oedema of both the left and right ventricles

associated with profound cardiac energetic impairment in the acute stages of takotsubo cardiomyopathy [Dawson et al, 2015; Scally et al, 2016]. As part of a multicentre study, we have demonstrated persistent abnormalities of cardiac inflammation and energetics after an acute episode of takotsubo cardiomyopathy using magnetic resonance spectroscopy [Scally et al, 2018; Scally et al, 2019]. This occurred despite a normalisation of the resting left ventricular ejection fraction and was associated with some persistent symptoms and cardiac limitation during cardio-pulmonary exercise testing [Scally et al, 2018; Scally et al, 2019].

In a previous Medical Research Council Clinical Research Training Fellowship ([name], MR/T029153/1), we have demonstrated that there was a profound reduction in myocardial manganese uptake in patients with takotsubo cardiomyopathy, and this was most marked immediately after the acute episode [Singh et al, 2022b]. Whilst there was some recovery in the longer term, there remained a marked residual reduction in myocardial manganese uptake (Figure 1). This suggests that perturbations in myocardial calcium handling may underlie the pathophysiology of takotsubo cardiomyopathy. Moreover, given the absence of a simple measure of ongoing left ventricular dysfunction in patients with takotsubo cardiomyopathy, manganese-enhanced magnetic resonance imaging represents an excellent potential quantitative surrogate biomarker to determine candidate pathways that could then be taken forward for further assessment.

**Figure 1**

Manganese-enhanced magnetic resonance imaging and T1 maps in healthy volunteers (A) and patients with takotsubo cardiomyopathy during the acute phase (B) and at 6-12 months after recovery (C). Compared to healthy volunteers, myocardial manganese uptake ( $K_i$ ) is markedly inhibited in patients with takotsubo cardiomyopathy, being nearly halved in the acute phase and remaining substantially reduced in the longer term (D).

#### ***4.3.3 Manganese-enhanced magnetic resonance imaging and role of sodium-glucose co-transporter***

We recently assessed the effect of sodium-glucose co-transporter 2 inhibition on myocardial manganese uptake in patients with heart failure. In this preliminary pilot double-blind randomised study, dapagliflozin but not placebo appeared to improve myocardial manganese uptake in these patients. We are currently extending this work, but together with the time-course studies in patients with takotsubo cardiomyopathy, these promising early data suggest that the sodium-glucose co-transporter 2 may have a role in regulating myocardial calcium handling. We now need to confirm this in cohorts of patients with takotsubo cardiomyopathy.

## **1.2 RATIONALE FOR STUDY**

We have recently demonstrated the proof-of-concept that manganese uptake is markedly impaired in patients with takotsubo cardiomyopathy, particularly in the acute phase but also in the longer term. This detection of covert left ventricular dysfunction is important because it provides a common pathophysiological indicator of the underlying dysfunction as well as providing a quantitative measure of disease activity.

We hypothesise that in patients with takotsubo cardiomyopathy:

1. Acute renin-angiotensin system activation but not beta-adrenoreceptor stimulation, causes impaired myocardial manganese uptake.
2. Chronic angiotensin receptor stimulation combined with vasoactive peptidases or sodium-glucose co-transporter 2 channels cause impaired myocardial manganese uptake.

## **2 STUDY OBJECTIVES**

### **2.1 OBJECTIVES**

#### **2.1.1 Primary Objective**

We propose to undertake experimental medicine studies in patients with acute or chronic takotsubo cardiomyopathy to explore whether neurohumoral activation or sodium-glucose transporters are implicated in the abnormal myocardial calcium handling of the left ventricle.

#### **2.1.2 Secondary Objectives**

As part of a planned subgroup analysis, we will undertake exploratory analyses to see if there are other factors that may determine myocardial

manganese uptake including cardiovascular risk factors. We will also explore the proportionate changes with acute versus chronic changes as well as compare the effectiveness of any reversal of altered myocardial calcium handling. We will also examine effects on cardiac and neurohumoral biomarkers to assess potential pathways of benefit. We will also explore correlations between myocardial manganese uptake and self-reported symptoms and objective assessments of exercise capacity.

## **2.2 ENDPOINTS**

### **2.2.1 Primary Endpoint**

Left ventricular myocardial manganese uptake.

### **2.2.2 Secondary Endpoints**

1. Assessing effects of renin-angiotensin system inhibition and beta-adrenoreceptor blockade on myocardial manganese uptake.
2. Assessing effects of angiotensin receptor/neprilysin inhibition and sodium-glucose co-transporter 2 inhibition on myocardial manganese uptake.
3. Assessing the effects of cardiovascular risk factors on myocardial manganese uptake.

[figure not shown]
### **2.2.3 Exploratory Endpoints**

1. Correlation of neurohumoral markers and myocardial manganese uptake.
2. Correlations between myocardial manganese uptake and self-reported symptoms and objective assessments of exercise capacity in Takotsubo Cardiomyopathy.

[figure not shown]
## **3 STUDY DESIGN**

This will be a prospective randomised open-label blinded endpoint (PROBE) study design with additional use of a cross-over design to improve statistical power. The following flow charts summarise what each study visit will involve for each different group of study participants.

**Study 1:**

**Study 2:**

Healthy volunteers:

Visit 1. 3 hours.  
Consent, clinical history and examination.  
Patient questionnaires, walking test and blood tests.  
Heart tests: ECG, heart ultrasound and MRI scan.  
3 hours.

## 4 STUDY POPULATION

### 4.1 NUMBER OF PARTICIPANTS

We aim to recruit 60 participants with an acute diagnosis (within 3 months) of takotsubo cardiomyopathy and 40 participants with a prior diagnosis (>6 months) of takotsubo cardiomyopathy as well as 20 age and sex-matched healthy volunteers. The study will end when the final participant attends for their final study visit. The expected length of recruitment period will be 24-30 months.

#### 4.1.1 Study 1: Patients with Acute Takotsubo Cardiomyopathy

We will recruit 60 patients with acute takotsubo cardiomyopathy and 20 age and sex matched healthy volunteers.

#### 4.1.2 Study 2: Patients with Prior Takotsubo Cardiomyopathy

We will recruit 40 patients with prior takotsubo cardiomyopathy (>6 months previously) for this second cohort of patients. We will recruit these patients contemporaneous with Study 1 so that we can use the same 20 age and sex matched healthy volunteers as a comparator.

### 4.2 INCLUSION CRITERIA

Takotsubo cardiomyopathy patients:

- Males and females >18 years of age
- Clinical presentation of takotsubo cardiomyopathy
- Have capacity to give formal consent

Healthy volunteers:

- Males and females >18 years of age
- Normal LV function
- No major co-morbidities such as ischaemic heart disease, heart failure, cancer or stroke
- Have capacity to give formal consent

### **4.3 EXCLUSION CRITERIA**

- Unable to tolerate or contraindication to magnetic resonance imaging
- Renal failure (estimated glomerular filtration rate <30 mL/min/1.73 m^2)
  - this would be assessed by performing a blood test
- Prior history of cardiomyopathy
- Current pregnancy
- Weight greater than 250kg
- Severe asthma for study 1 (given Bisoprolol is contraindicated in this condition)
- Type 1 diabetes mellitus for study 2 (given Dapagliflozin is contraindicated in this population)
- Significant hypotension (given the medications prescribed as part of the study can also cause hypotension as a side effect)
- Significant bradycardia for study 1 (given Bisoprolol can exacerbate any pre-existing significant bradycardia)
- Prescribed Digoxin (this medication interacts with the Manganese)
- Unable to give formal consent

### **4.4 CO-ENROLMENT**

Co-enrolment with other studies may be considered in line with ACCORD co-enrolment policy. Co-enrolment between studies will be agreed by the respective PIs prior to beginning of the study. Individual patients who are eligible for co-enrolment will be discussed between research fellows and PIs as necessary. This will ensure co-enrolment:

1. Is appropriate (i.e. there are no contra-indications)
2. Would not jeopardise the integrity of either study
3. Would not compromise patient care and safety

## **5 PARTICIPANT SELECTION AND ENROLMENT**

### **5.1 IDENTIFYING PARTICIPANTS**

For Study 1, potential participants will be identified by the co-investigator, who will be part of the patients' cardiology clinical care team. This will happen either whilst the participant is still in hospital or shortly after discharge. The co-investigator will provide an information sheet if the participant is interested in taking part in the study.

For Study 2, the co-investigator will identify participants via the Scottish National Takotsubo registry. PBPP and REC approvals are in place to obtain the contact details of patients identified as part of the Scottish Takotsubo Registry so that we can invite them to take part in research. Participants will also be identified by the patients' usual clinical care team when they attend for cardiology clinic follow-up. If they meet inclusion criteria they will be invited to take part in the study and their information and contact details passed on to the co-investigator who will contact them to arrange an initial study visit.

In addition to NHS Lothian, participants can be approached within the NHS Greater Glasgow and Clyde health board. Participants will be approached at the Golden Jubilee National Hospital which will act as a Participation Identification Centre (PIC). Participants will be approached in the usual way, by their usual clinical care team either whilst they are in hospital as an inpatient or at an outpatient clinic. All study activities including patient consent will still take place at the original research site at the University of Edinburgh. There is funding in place to ensure that patients travelling to Edinburgh from Glasgow are offered reimbursement for the cost of travel to the study site.

Healthy volunteers will be recruited via an advertisement process.

## **5.2 CONSENTING PARTICIPANTS**

Participants will be enrolled following an opportunity to read the patient information sheet and ask questions. Informed consent can be taken by any of the study investigators and they will also decide if patients are eligible. Once written informed consent is obtained, screening for eligibility can begin. A screening log will be maintained which will contain anonymised data and will be kept in on Excel spreadsheet on a password-locked University of Edinburgh laptop. Consent will be confirmed at the beginning of any study activities.

## **5.3 WITHDRAWAL OF STUDY PARTICIPANTS**

Participants are free to withdraw from the study at any point or a participant can be withdrawn by the Investigator. If withdrawal occurs, the primary reason for withdrawal will be documented if possible. The participant will have the option of withdrawal from all aspects of the study but continued use of data collected up to that point. To safeguard rights, the minimum personally identifiable information possible will be collected. If participants withdraw from the study, they will not need to be replaced.

## 6 INTERVENTIONS

### 6.1 STUDY MEDICATION

#### 6.1.1 Identity of study medication

Study Medication	Medication form, dose and usual indication	Manufacturer
Bisoprolol	Oral tablet 2.5 mg once daily Dose increased to 5mg after 1 week then increased to 10mg after another 1 week Usual indication: Heart failure, hypertension, arrhythmias	Alliance Healthcare
Valsartan	Oral tablet 80 mg twice daily Dose increased to 160mg twice daily after 1 week Usual indication: Heart failure, hypertension	Alliance Healthcare
Sacubitril/Valsartan	Oral tablet 24/26 mg twice daily Dose increased to 49/51mg after 1 week then increased to 97/103mg after 1 week Usual indication: Heart failure	Novartis
Dapagliflozin	Oral tablet 10 mg once daily Usual indication: Heart failure, type 2 diabetes mellitus	AstraZenaca

#### 6.1.2 Doses and treatment regimens

Patients in study 1 will be randomised 1:1:1 to no treatment, or open-label valsartan or bisoprolol.

Patients in study 2 will receive 3 months treatment with combination sacubitril and valsartan and dapagliflozin 10 mg in random order. This will be separated by a one-month medication “wash out period.”

Medications will be prescribed on a research specific prescription form by a co-investigator in the Clinical Research Facility. The medication will then be dispensed “off the shelf” from the Royal Infirmary of Edinburgh pharmacy department.

Randomisation will take place by block randomisation. An unbiased colleague will create the blocks for randomisation and the study investigators will be blinded to the blocks until the point of randomisation.

### **6.1.3 Storage**

Study drugs will be stored in the pharmacy department, as per an agreement with the lead research pharmacist at the Royal Infirmary of Edinburgh. The pharmacy department will ensure that medications are stored as per manufacturer instructions.

## **6.2 CONCOMITANT AND POST-STUDY INTERVENTIONS**

Following completion of the study, the study medications will be discontinued. For bisoprolol, the dose will be slowly down titrated before complete discontinuation. We aim to reduce the Bisoprolol dose by 2.5mg each week. All other study medications will be safe to stop immediately.

If participants are already prescribed medication which is the same, similar to or interacts with the study medication then one or more of their current medications may be changed. This would only be considered if it was safe to do so and after an informed discussion with the participant. In some cases, an alternative medication may be offered. At the end of the study, we will have a further discussion with participants regarding their medication. If we have discontinued a medication at the start of the study, this may be restarted again, but we will assess this on a case-by-case basis. We will inform the participants' GPs which medication they should be prescribed at the end of the study.

## **6.3 COMPLIANCE WITH STUDY INTERVENTIONS**

The investigators will assess treatment compliance at attendance of each of the study visits by pill counting at each visit after randomisation.

### **6.3.1 Accountability**

Compliance will be assessed by interview and pill counting. If the patient is suspected to have taken a medication overdose they will undergo immediate clinical assessment by one of the co-investigators. This will include checking their heart rate, blood pressure and performing a clinical examination. They may also require blood tests. If there is any concern, the co-investigator will arrange for the patient to be admitted to hospital. If an overdose occurs this will be recorded as a Significant Adverse Event.

## 6.4 DISCONTINUATION OF STUDY MEDICATION

The study medication will be discontinued under the following circumstances:

1. At the request of the patient or if the patient withdraws from the study.
2. By the investigator or the responsible clinician if this was felt to be in the best interests of the patient.
3. On completion of the study.

The patient will be asked to return any unused study medication to the pharmacy department at the Royal Infirmary of Edinburgh.

### 6.4.1 Procedures for discontinuation of a subject from study medication

Brief interruptions of therapy will be permitted (<14 days) where there is a clinical need. If medication needs to be stopped for longer than 14 days then the patient will be withdrawn from the study. This will be documented in patients' medical records. Reasons for interruption or discontinuation of study medications include side effects of medications. The table below summarises some side effects associated with the study medication:

Study Medication	Potential side effects
Bisoprolol	Hypotension, bradycardia, erectile dysfunction, rash, cold peripheries
Valsartan	Hypotension, impaired renal function, nausea, diarrhoea, rash
Sacubitril/Valsartan	Hypotension, impaired renal function, nausea, diarrhoea, rash
Dapagliflozin	Diabetic ketoacidosis, genital infections (only applies to patients with type 2 diabetes mellitus)

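### Stopping study drug for more than 14 days means leaving the study, so in Study 1 later scans can be lost by rule from the drug arms only

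*Protocol*

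**What the plan says.** Section 6.4.1 of the protocol allows short gaps in treatment: "Brief interruptions of therapy will be permitted (<14 days) where there is a clinical need". For longer gaps it says: "If medication needs to be stopped for longer than 14 days then the patient will be withdrawn from the study". It names tolerability as a cause: "Reasons for interruption or discontinuation of study medications include side effects of medications". (A gap of exactly 14 days falls under neither sentence, and the two should be reconciled.)

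Section 5.3 adds: "If participants withdraw from the study, they will not need to be replaced". On data already gathered it says: "The participant will have the option of withdrawal from all aspects of the study but continued use of data collected up to that point". No section provides for a scan after withdrawal.

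On design, section 6.1.2 says of Study 1: "Patients in study 1 will be randomised 1:1:1 to no treatment, or open-label valsartan or bisoprolol". Of Study 2 it says: "Patients in study 2 will receive 3 months treatment with combination sacubitril and valsartan and dapagliflozin 10 mg in random order". Section 4.1.1 sets the Study 1 size: "We will recruit 60 patients with acute takotsubo cardiomyopathy and 20 age and sex matched healthy volunteers". The primary endpoint (section 2.2.1) is left ventricular manganese uptake. The visit tables in section 7.2 schedule the manganese scan at baseline, 4 weeks and 3 months in Study 1, and at baseline, 3 months and 7 months in Study 2.

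**The concern.** Coming off a drug and leaving a trial are different events, and the protocol makes the first cause the second. In Study 1 this works on one side only. A patient on valsartan or bisoprolol who stops for more than 14 days has no 3-month scan, and no 4-week scan either if the stop comes early. An untreated patient cannot meet the condition. If tolerance of these drugs is related to manganese uptake, those still scanned at 3 months in the drug arms are a selected group set against an unselected control group, and randomisation no longer protects the comparison.

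In Study 2 the problem is different. Someone withdrawn during period 1 never reaches the second drug or the 7-month scan, and so drops out of the within-person comparison on which section 10.1 rests its claim of extra precision.

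An analysis plan can define populations and missing-data methods, but it cannot recover scans that the protocol does not collect.

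**Working it through.** **Inputs from the protocol.** Target effect 0.6 mL/100 g/min, 90% power, two-sided 0.05, 18 per group, patient SD 0.5 (section 10.1); 60 Study 1 patients allocated 1:1:1, so 20 per arm (sections 4.1.1 and 6.1.2).

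**Inputs assumed.** The protocol gives neither a stopping rate nor a correlation between tolerance and uptake. I take 20% and 30% of a drug arm stopping, and correlations r of 0, 0.3 and 0.5.

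**1. The plan's own figure.** For a two-sample t-test of 0.6 at 90% power:
- SD 0.5 gives 15.62, so 16 per group.
- SD 0.54 gives 18.04, essentially the stated 18.

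The SD behind the 18 is not stated, so I carry both 0.5 and 0.54.

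**2. Selection bias.** Suppose there is no drug effect and the least tolerant fraction p leaves. The mean of those remaining shifts by

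r × SD × φ(z_p) / (1 − p),

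where z_p is the normal p-quantile and φ the normal density.
- p = 0.2: φ(−0.842)/0.8 = 0.280/0.8 = 0.350.
- p = 0.3: φ(−0.524)/0.7 = 0.348/0.7 = 0.497.

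| Drug arm lost | r | Shift (SD 0.5) | Share of 0.6 | Simulated type I error |
|---|---|---|---|---|
| 20% | 0 | 0 | 0% | 0.052 |
| 20% | 0.3 | 0.3 × 0.5 × 0.350 = 0.052 | 9% | 0.059 |
| 20% | 0.5 | 0.5 × 0.5 × 0.350 = 0.087 | 15% | 0.078 |
| 30% | 0 | 0 | 0% | 0.051 |
| 30% | 0.3 | 0.3 × 0.5 × 0.497 = 0.075 | 12% | 0.067 |
| 30% | 0.5 | 0.5 × 0.5 × 0.497 = 0.124 | 21% | 0.106 |

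The last column comes from 40,000 simulated null trials per row, with 20 untreated patients against those remaining of 20 treated. The direction of the shift follows the sign of the correlation.

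**3. Power, with losses in the drug arm only.** Noncentrality is 0.6 / (SD × √(1/20 + 1/n)), with 18 + n degrees of freedom.
- 20 v 16: 0.6/(0.5 × 0.3354) = 3.58, power 93.5%. At SD 0.54: 3.31, power 89.6%.
- 20 v 14: 0.6/(0.5 × 0.3485) = 3.44, power 91.6%. At SD 0.54: 3.19, power 87.1%.

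**4. Cost of scanning everyone.** In the worst case 20% of the drug arm is fully off drug, with no residual effect, when scanned. The as-randomised effect is then 0.8 × 0.6 = 0.48. At 20 v 20:
- SD 0.5: 0.48/(0.5 × 0.3162) = 3.04, power about 84%.
- SD 0.54: 0.48/(0.54 × 0.3162) = 2.81, power about 78%.

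These two figures hold the SD fixed. Mixing on-drug and off-drug patients would widen the drug-arm SD somewhat, for example to √(0.25 + 0.2 × 0.8 × 0.36) = 0.555, so they are slightly favourable.

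**The case against.** Several points on the other side have force.

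- **The bias rests on assumptions.** With no correlation there is none, and its sign is unknown. The side effects tabulated in section 6.4.1 include rash, nausea and cold peripheries, which have no evident link to uptake, as well as hypotension and bradycardia, which might. Section 4.3 already excludes significant hypotension and, for Study 1, significant bradycardia and severe asthma, which should reduce stopping. This stands: the size is conditional.
- **An on-drug effect is a defensible target** for an experimental medicine study asking whether a pathway is involved. This also stands, and is why the on-treatment analysis should be kept. It does not remove the one-sided selection.
- **The remedy has a price.** At 20% stopping, the worst-case dilution of 0.12 is larger than the 0.05-0.09 bias. This stands, though dilution is an understood attenuation of a different quantity, whereas the bias has unknown direction.

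A reader might also infer more than the text supports. The drug arms are not simply reduced to patients who tolerate treatment: gaps under 14 days are allowed, data before withdrawal may be kept, and later stoppers still have a 4-week scan. The contrast with an untreated arm does not extend to Study 2, where a period-2 stopper keeps the baseline and 3-month scans. Nor does the rule clearly use up a dropout allowance for the treatment arms, since section 10.1 words the increase to 20 for healthy volunteers only.

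**Conclusion.** The concern holds as a matter of design. A stated rule can remove later primary-endpoint scans from the drug arms of Study 1 and cannot touch the untreated arm. In Study 2 it costs period-1 stoppers their place in the paired comparison. Under the assumed 20-30% stopping and correlation of 0.3-0.5, the shift is 0.05-0.12, or 9-21% of the target effect; it could be nil, or run in either direction.

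It would be wrong to read this as a threat to power. With 30% of one drug arm lost, power is still 91.6% (SD 0.5) or 87.1% (SD 0.54), against a planned 90%. The case rests on selective loss of data. Because the size is unknown and early data are kept, this is something the sponsor should fix; it does not by itself invalidate the trial.

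**What to change.** Amend section 6.4.1, with section 5.3 to match, so that stopping study drug is separate from leaving the study:

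- Participants who stop for more than 14 days and still consent attend the remaining scheduled manganese scans under their randomised allocation.
- For Study 2, state which scans are kept for those who stop in period 1. Whether they start the second drug stays with the investigator's clinical judgement.
- Report the as-randomised comparison alongside an on-treatment analysis that uses the 14-day criterion.

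Decisions on when to stop a drug are unchanged. The cost is a short amendment; the scans are already in the visit schedule. The statistical price is dilution of the as-randomised effect, with the worst case shown above, while the on-treatment result that the present rule would yield remains available. The amendment should come early, because missed scans cannot be recovered.
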